2.m. Sample Size/Data Analyses. We will randomize about 2100 men (700 per arm), expecting 70% retention over the 9-month follow-up (based on our pilot study). We are confident in reaching this sample size given the large number of YSMM on social media and that similar sample sizes have been recruited via social media.^{64,65} All analyses will use an intent-to-treat approach.

Aim 1 (Efficacy). We hypothesize HPV vaccine initiation and completion will be higher among participants in both the Out-U and Out-I groups compared to participants in the control group (Hypothesis 1a). Further, we hypothesize that HPV vaccine initiation and completion will be higher among participants in the Out-I group compared to participants in the Out-U group (Hypothesis 1b).

We will first examine descriptive statistics (i.e., proportions and 95% confidence intervals [CIs]). We will then use logistic regression to test our hypotheses, with separate models for HPV vaccine initiation and completion. Models will control for any potential confounders (i.e., variables that differ between study arms [$p < 0.10$] at baseline). For each outcome, we will perform all pairwise comparisons of study arms, using a Bonferroni corrected two-sided alpha of 0.017 to control the overall type I error rate. We will have at least 80% power for all comparisons,⁶⁶ assuming our

projections of initiation (control=20%; Out-U=35%; Out-I=45%) and completion (control=10%; Out-U=22%; Out-I=35%). Projections are based on pilot study results and past work on different types of reminders.^{67,68} Logistic regression models will produce odds ratios (ORs) and 95% CIs. Results will determine the efficacy of *Outsmart HPV* and identify which type of HPV vaccine reminder most effectively increases vaccination.

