Aim 2 (Mediation). We will examine all theoretical constructs as potential mediators (see Section 2.n.). We hypothesize the effects of the intervention will be mediated by changes in theoretical constructs, including increased perceived vulnerability to HPV and HPV-related disease, reduced response costs of getting HPV vaccine (e.g., reduced concerns about vaccine safety and side effects), increased self-efficacy to get HPV vaccine, and increased intention to get HPV vaccine (Hypothesis 2). This hypothesis is based on our pilot study results, where *Outsmart HPV* caused larger changes in each of these constructs than the control group.⁶⁹ We expect mediators will be similar for both HPV vaccine initiation and completion.

To test this hypothesis and identify mediators, we will use structural equation modelling (SEM). SEM has several advantages over standard regression analyses, including the ability to assess multiple potential pathways in one model.⁷⁰ We will examine HPV vaccine initiation and completion separately and use a probit link to transform each binary outcome to a standard Normal scale.⁷⁰ For each outcome, we will fit two models using a maximum likelihood approach: a “full” model and a more parsimonious “final” model. The “full” model will include study arm, all theoretical constructs, and an outcome variable. We will examine the overall model fit of the “full” model via the Root Mean Square Error of Approximation (RMSEA) and other metrics (chi-square test, etc.).^{71,72} We will consider a RMSEA<0.07 to indicate acceptable fit.⁷² To create the “final” model, we will remove pathways (i.e., associations) from the “full” model based on effect size and the chi-square test for nested models. This process will continue until removing pathways no longer improves the model. The resulting model will be the “final” model. SEM models will produce standardized path coefficients that estimate the direct and indirect effects of study arm and the theoretical constructs. Given our analytic sample size, we will have at least 90% power to rule out RMSEA>0.08 with 95% confidence. Results will identify which changes in theoretical constructs are the key drivers of *Outsmart HPV* increasing HPV vaccination.

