Aim 3 (Moderation). We will examine demographic and health-related characteristics from the screener and T1 surveys as potential moderators. We hypothesize intervention effects will be stronger (i.e., moderation) among YSMM who are not married or in a relationship (due to higher perceived vulnerability to HPV and HPV-related disease), live in urban areas (due to greater access to care, including LGBT-friendly providers), report having a routine medical check-up in the last year (due to higher utilization of healthcare and self-efficacy to get HPV vaccine), or report having disclosed their sexual orientation to a healthcare provider (due to higher self-efficacy to talk with a healthcare provider about HPV vaccine) (Hypothesis 3). We expect moderators will be similar for both HPV vaccine initiation and completion (which will be examined as separate outcomes).

We will use logistic regression models that include an interaction term between each potential moderator and study arm to test this hypothesis and identify moderators. Logistic regression models will produce ORs and 95% CIs. We will consider an interaction present if an interaction term has $p<0.05$. Given our analytic sample size, we will have 80% power to detect interaction terms with ORs>2.30. Results will determine if intervention efficacy differs by demographic and health-related characteristics.

2.n. Potential Challenges. Recruitment: We have expertise recruiting YSMM via social media^{26,44,73-77} and will offer study incentives. **Retention:** We expect 70% retention based on our pilot study and will provide incentives and survey notifications to aid retention. **Missing data:** Missing survey data will be minimized by using prompts for skipped items. This resulted in less than 5% missing data in our pilot study. **Outcome ascertainment:** HPV vaccination status will be confirmed by medical records if MRR is provided, otherwise self-reported data will be used. **Generalizability:** To maximize

generalizability, participants will be recruited throughout the US. YSMM recruited via Facebook in our pilot study were demographically similar to YSMM from nationally representative samples.²⁶⁻²⁸ **Contamination:** We do not expect contamination since we will recruit throughout the US, the project website will require login, and participants will receive only the study materials for their randomized study arm.

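### Aim 1: testing every pairwise comparison at a fixed 0.017 is valid within each outcome but gives up power for Out-I vs Out-U on initiation that Holm would recover at the same 5% limit

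*Combined protocol and SAP*

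**What the plan says.** Section 2.m, Aim 1, fits logistic regression "with separate models for HPV vaccine initiation and completion". The testing rule is: "For each outcome, we will perform all pairwise comparisons of study arms, using a Bonferroni corrected two-sided alpha of 0.017 to control the overall" (the quantity controlled is the type I error). The arm projections (control / Out-U / Out-I) are 20 / 35 / 45% for initiation and 10 / 22 / 35% for completion, and at least 80% power is claimed for all comparisons. The section randomizes 700 per arm, "expecting 70% retention over the 9-month follow-up", and adds: "All analyses will use an intent-to-treat approach". It does not say how many participants per arm enter the analysis or how a missing vaccination outcome is counted.

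On estimation: "Logistic regression models will produce odds ratios (ORs) and 95% CIs". One stated purpose of the Aim 1 results is to "identify which type of HPV vaccine reminder most effectively increases vaccination".

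The two outcomes are kept apart throughout. Aim 2 says "We will examine HPV vaccine initiation and completion separately", and Aim 3 says of the same two outcomes "which will be examined as separate outcomes". Control within each outcome is therefore the plain reading of the Aim 1 sentence. No stepwise procedure is mentioned.

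**The concern.** All three comparisons of an outcome are held to 0.017 whatever the other two show. If both active arms clearly beat control, the only null hypothesis still in doubt is Out-I = Out-U. It could then be tested at 0.05 without exceeding 5% for that outcome, yet the plan still tests it at 0.017. That comparison is Hypothesis 1b, it bears directly on the choice of reminder type, and on initiation it is the weakest of the six at the projections.

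Two statements are also missing:

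- The plan does not say in so many words that the overall error rate is controlled within each outcome and not across both.
- It does not say that the 95% intervals are unadjusted while the tests use 0.017. An interval can exclude an odds ratio of 1 while the planned test is not significant, and the reader is not told how to take that.

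**Working it through.** **Inputs (section 2.m).** 700 randomized per arm, and 0.70 × 700 = 490 retained; the projections above; two-sided alpha 0.017 (0.05/3 = 0.0167, rounded).

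**Step 1: the plan's own power claim.** For two proportions with n per arm and a pooled-variance test,

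power = Φ[(|p₂ − p₁| − z·SE₀)/SE₁], where SE₀ = √(2p̄(1 − p̄)/n) and SE₁ = √((p₁(1 − p₁) + p₂(1 − p₂))/n).

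Out-I vs Out-U, initiation, n = 490:
- p̄ = 0.40, SE₀ = √(0.48/490) = 0.03130, SE₁ = √(0.475/490) = 0.03113.
- At 0.017 (z = 2.387): (0.10 − 0.0747)/0.03113 = 0.81, power **79.2%**.
- At 0.05 (z = 1.960): (0.10 − 0.0613)/0.03113 = 1.24, power **89.3%**.

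The other five comparisons at 0.017 and n = 490 are:
- initiation: 99.8% (Out-U vs control) and 100% (Out-I vs control);
- completion: 99.7% (Out-U vs control), 100% (Out-I vs control) and 98.4% (Out-I vs Out-U).

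With n = 700 the weakest comparison has 92.5%. The claim of at least 80% therefore reproduces to within a point at 490 and is exceeded at 700.

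**Step 2: validity of the planned rule.** With all three arms equal, simulated error per outcome is about 4.4% under fixed 0.017 and about 4.4% under Holm. The bound 3 × 0.017 = 5.1% exceeds 5% only through rounding. Over both outcomes the error is about 7.7% under either rule, but the plan does not clearly claim to control that.

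**Step 3: Holm.** Order the three p-values of an outcome. Compare the smallest with 0.05/3, the next with 0.05/2 and the largest with 0.05, stopping at the first failure. Holm rejects everything that Bonferroni at exactly 0.05/3 rejects, and can reject more. At the projections both comparisons with control are almost always rejected, so Out-I vs Out-U is in effect tested at 0.05.

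Simulated power for Out-I vs Out-U on initiation (pooled z-tests, at least 200,000 trials per setting). The analysed numbers are assumptions.

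| Setting (control / Out-U / Out-I) | n per arm | Fixed 0.017 | Holm |
|---|---|---|---|
| Projections 20/35/45% | 490 | 79% | 89% |
| Projections, 85% analysed | 595 | 87% | 94% |
| Projections, all analysed | 700 | 92% | 97% |
| 30% missing counted as unvaccinated (rates × 0.7: 14/24.5/31.5%) | 700 | 70% | 83% |
| Out-U equal to control, 35/35/45% | 490 | 79% | 82% |
| Half the projected differences, 20/27.5/32.5% | 490 | 25% | 36% |

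In the half-effect setting, Out-U vs control rises from 65% to about 73%.

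A check with the planned type of model used logistic regression with Wald tests. It assumed ten baseline variables, two of them prognostic, and entered those with p < 0.10 across arms. Over 6,000 trials per setting it gave 79.2% vs 89.0% at 490 and 91.9% vs 96.9% at 700.

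**Step 4: the price.**
- Out-U equal to Out-I, both better than control (20/35/35% and 10/22/22%): false claims between them rise from 1.7% to about 5% per outcome, and from about 3% to 8% over both outcomes. They are two-sided, so about half would favour Out-I.
- Out-U equal to control, Out-I better (35/35/45%, n = 490): false Out-U vs control claims rise from about 1.7% to 3.7%.

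**Step 5: intervals against tests.** An unadjusted 95% interval excludes 1 while the fixed-0.017 test fails when 0.017 < p ≤ 0.05. For this comparison at the projections that happens in about 10% of trials at 490, 4% at 700 and 13% with missing counted as unvaccinated. Under Holm, p ≤ 0.05 without rejection is about 0% at the projections, 4% at half effects and 7% with Out-U equal to control (the last two at 490).

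**The case against.** The strongest reply is that nothing is wrong. The plan fixes its comparisons, alpha and projections in advance, the rule controls error within each outcome, and the 80% target is essentially met. Only one of six comparisons gains materially, and Hypothesis 1b is also tested on completion with about 98% power. All of that stands, and it is why the point is minor.

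A second reply is that the gain is a trade on one contrast: more power if Out-I is better, three times the false claims if it is not. Out-U is the pilot intervention, and Out-I adds staff who answer messages by hand, so a stricter threshold before preferring Out-I is a defensible choice. This also stands as a reason the investigators might keep 0.017. It does not make Holm unsound, because the higher figure stays within the 5% per outcome that the plan itself sets.

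Third, Holm is not the most powerful option. With three arms, once one equality is false at most one of the other two can be true, so Shaffer's step-down may test both remaining comparisons at 0.05. At 35/35/45% and 490 per arm it gives about 85% against Holm's 82%. At the projections the two coincide, so the main result is unaffected.

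Fourth, fixed Bonferroni has simple matching simultaneous intervals (1 − 0.05/3 = 98.3%) and Holm does not. This loss is small here, because the plan reports ordinary 95% intervals anyway.

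**Conclusion.** The point holds as a minor efficiency improvement, not an error. The planned rule is valid and its power claim essentially reproduces. Holm within each outcome keeps the same 5% limit and lifts Out-I vs Out-U on initiation from just under the 80% target to well above it at 490 per arm: the chance of missing the projected difference falls from about 21% to 11%. At 700 per arm it falls from about 8% to 3%.

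These sizes rest on the plan's projected rates and on an assumed analysed number, which the plan does not give. The gain shrinks to about 3 points if Out-U equals control with the 35% vs 45% contrast kept. The cost is a rise from 1.7% to about 5% per outcome in false claims between the two active arms when they are truly equal. The two missing statements would not carry the point alone, but they are needed under either rule.

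**What to change.** In section 2.m, Aim 1, replace the multiplicity sentence with wording such as:

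> Within each outcome (initiation, completion), the three comparisons between arms will be tested by the Holm procedure at a two-sided familywise level of 0.05: smallest p-value against 0.05/3, next against 0.05/2, largest against 0.05, stopping at the first non-significant result. There is no adjustment across the two outcomes. Confidence intervals for odds ratios are 95% and not adjusted for multiplicity.

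If the investigators prefer the lower risk of a false Out-I vs Out-U claim, keep 0.017 and add only that control is within each outcome and that the intervals are unadjusted.

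The change is to analysis wording only; sample size and data collection are untouched. Because Holm is the more liberal rule, it should be fixed before anyone sees outcome data by arm. The document is dated March 8, 2021 and does not say how far the trial had run, so the date of the change should be recorded against that point.

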2.c. T1 Survey. After project account setup, participants will begin their initial project website session, which will include completing the T1 (baseline) survey, viewing study materials online (either *Outsmart HPV* or control), and completing the T2 survey. The T1 survey will be completed on the project website and assess demographics, health characteristics, and theoretical constructs (about 15 minutes in duration; see Appendix). All survey items will be based on those used in past research.^{19,29-35} For all survey items (for the T1-T4 surveys), a reminder will appear if a participant tries to skip an item. The reminder will say, "Please answer each question." If participants still want to skip a question after the reminder is shown, they will be allowed to. For a few items, as indicated in the appendices included with this application, participants will be required to answer the question.

2.d. Randomization. Participants will next be randomized at the individual-level to a study arm: a) standard information about HPV and HPV vaccine (control group); b) *Outsmart HPV* that includes unidirectional vaccine reminders (Out-U); or c) *Outsmart HPV* that includes interactive vaccine reminders (Out-I). A 1:1:1 allocation scheme will be used, with assignments determined by an algorithm on the project website. Recruitment will continue until 2100 YSMM are randomized (700 per study arm).

2.e. Control Group. The control group will receive standard information about HPV and HPV vaccine (see Appendix). This content will be modeled after the Vaccine Information Statement (VIS) for HPV vaccine³⁶ (created by the Centers for Disease Control and Prevention) and viewed by control group participants on the project website. The VIS provides basic information about HPV and HPV vaccine. We modeled the control group content after the VIS because providers are required to give patients a VIS before vaccination.³⁶ Thus, the VIS may be considered the "standard of care." A printable version of this content will be available to control group participants for viewing/printing following completion of the T2 survey. If they wish, control group participants will also have the ability to log back into the portal after the T2 survey to view this content again (see Appendix for Re-accessing Information).

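### Aim 2 mediation model: no T1 adjustment or baseline covariate is stated, so the non-randomised construct-to-vaccination path is left open to confounding by baseline standing

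*Combined protocol and SAP*

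**What the plan says.** Section 2.m., Aim 2 (Mediation), sets out a full model that "will include study arm, all theoretical constructs, and an outcome variable". Initiation and completion are modelled separately, and the plan will "use a probit link to transform each binary outcome to a standard Normal scale". The final model comes from the full one by deleting pathways "based on effect size and the chi-square test for nested models"; no step adds a term.

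Hypothesis 2 is that "the effects of the intervention will be mediated by changes in theoretical constructs". The plan does not say whether this means a change score, a later value adjusted for T1, or a later value alone. The rationale is a pilot in which the intervention "caused larger changes in each of these constructs than the control group". The conclusion to be drawn is causal: "Results will identify which changes in theoretical constructs are the key drivers of" the intervention's effect on vaccination.

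The T1 survey, completed before randomisation, will "assess demographics, health characteristics, and theoretical constructs" (Section 2.c.). Constructs are measured again at T2, straight after the materials are viewed (Section 2.h.), and at T3 and T4, in the same surveys that ask about vaccination (Section 2.i.). The only confounder rule in the plan is under Aim 1 and picks variables that differ between arms at baseline with p<0.10.

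**The concern.** A mediated effect is the product of two paths. Arm to construct is randomised. Construct to vaccination is an observational association within arms. A man with high intention or self-efficacy at T1 will tend to have it later too, and may be more likely to be vaccinated for reasons that the later score does not carry.

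The plan itself points to possible common causes. Under Aim 3 it links a recent check-up and disclosure to a provider with self-efficacy, and relationship status with perceived vulnerability. Self-efficacy and vulnerability are both Hypothesis 2 mediators. Check-up and disclosure could plausibly also affect access to vaccination, yet none of the three is listed as a covariate for Aim 2.

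The Aim 1 rule does not fill the gap, because a variable can confound construct and outcome while being perfectly balanced across arms. What is at stake is the list of constructs reported as driving the effect, and so what a later version of the intervention would concentrate on.

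**Working it through.** **The plan's own figure.** Aim 2 claims at least 90% power to rule out RMSEA above 0.08 with 95% confidence. It gives neither model degrees of freedom nor a true RMSEA, so the figure cannot be strictly reproduced. With 70% of 2100 retained (1470 men), a noncentral chi-square calculation reaches 90% power with at least 2 degrees of freedom if the true RMSEA is 0, at least 7 if it is 0.05, and at least 16 if it is 0.06. The claim is plausible, but it concerns fit, and fit cannot reveal a confounder that is left out of the model.

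**Direction of the bias.** Let M1 be the T1 construct, M2 the later construct, X the arm and Y* the probit-scale propensity to vaccinate. Within arm, M1 and M2 have unit variance.

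- M2 = r·M1 + a·X + e
- Y* = b·M2 + c·M1 + (arm effect) + error

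Here b is the path of interest and c is the effect of T1 standing that bypasses M2. Within arm:

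- Levels only: slope = cov(M2, Y*)/var(M2) = b + c·r.
- Change only: cov(M2−M1, Y*) = (b−c)(1−r) and var(M2−M1) = 2(1−r), so slope = (b−c)/2.
- M2 with M1 as covariate: slope = b.

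With b = 0.20, c = 0.3 and r = 0.6:

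- levels 0.20 + 0.3×0.6 = 0.38
- change (0.20−0.30)/2 = −0.05
- T1-adjusted 0.20

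Probit simulation gives 0.37, −0.05 and 0.20; the small shortfall from 0.38 is probit rescaling.

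**How often a non-mediator is named.**

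Inputs from the plan: 490 per arm (70% of 700), and initiation of about 20% in control and 35% with the intervention (the control and Out-U projections).

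Assumed, because the documents give no values: arm effect on the construct 0.3 SD; r 0.5–0.7; c 0–0.3 probit units per SD. A construct counts as a mediator when both paths have |z| > 1.96, which is not the plan's rule.

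The table has b = 0, 490 control men against 980 intervention men (both intervention arms pooled at the same rate), and 400 runs per row.

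| r | c | Levels only | Change only | T1-adjusted |
|---|---|---|---|---|
| 0.5 | 0 | 5% | 5% | 5% |
| 0.5 | 0.1 | 31% | 33% | 6% |
| 0.5 | 0.2 | 83% | 81% | 4% |
| 0.5 | 0.3 | >99% | 98% | 5% |
| 0.7 | 0 | 4% | 6% | 5% |
| 0.7 | 0.1 | 55% | 18% | 5% |
| 0.7 | 0.2 | 99% | 55% | 4% |
| 0.7 | 0.3 | >99% | 88% | 5% |

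In the change-score column the false path has the wrong sign. With 490 against 490, the range for c = 0.1–0.3 is about 15% to nearly 100% unadjusted and about 4–7% adjusted.

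**A true mediator** (b = 0.20, r = 0.5, c = 0.2): levels give 0.30, the change score gives 0.00 and is declared in 5% of runs, and T1 adjustment gives 0.20. With c = 0 the change score still halves the path, to 0.10.

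**Limits.**

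- If arm does not move the construct, false naming is 0–3%.
- If an unmeasured common cause of construct and vaccination is added (probit effect 0.2), false naming is 82% even after T1 adjustment.
- If the constructs are measured with assumed reliability 0.7–0.8 (c = 0.3, r = 0.6–0.7), it is roughly 11–30% after adjustment.

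**The case against.** The strongest reply is that silence is not exclusion. The model list names no time points, constructs are measured four times, and a hypothesis about changes needs T1 in some form. A model with T1 constructs as covariates would fit the wording. Disclosure may even be in already, since Section 1.b. counts concealment of sexual orientation among the framework constructs. The construct list cannot be checked: the Aim 2 pointer to Section 2.n. leads to Potential Challenges, which defines none, and Figure 1 and the survey appendices are not available here. This stands in part. A reader might infer that the plan rules T1 out and that the path is therefore certainly confounded; the documents support neither. They do leave open two readings, levels only and bare change, that are generally biased if T1 standing has a direct effect.

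Nor is bias inevitable. Levels only is unbiased when c = 0, and change only when c = −b. No document gives c, r or the arm effect on a construct.

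The simulation is also not the planned analysis. The plan has three arms, fits all constructs together and prunes by effect size and nested chi-square. Other constructs in the model might absorb some baseline standing; this was not examined. The percentages show the mechanism and should not be read as this trial's error rate.

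Finally, the 4–7% after adjustment follows from making T1 the only confounder and measuring it without error. A reader might conclude that T1 adjustment makes the causal claim safe. It does not, as the 82% figure shows, and it does not repair the order of events when T3 or T4 constructs are recorded alongside vaccination status.

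**Conclusion.** The concern holds as a gap that leaves the construct-to-vaccination path open to confounding by baseline standing, together with an unnamed mediator time point. It is more than missing detail: the listed contents include no baseline term, the pruning rule cannot add one, and the conclusion is causal.

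Direction follows from the algebra. Levels only is biased upward when the direct T1 effect is positive; a bare change score generally errs the other way. Size rests on assumption: roughly 15% to nearly 100% false naming for direct T1 effects of 0.1–0.3, about 4–7% with T1 adjustment, and near 5% in every version when that effect is zero. False naming also needs the intervention to move the construct, which the pilot statement makes likely for the hypothesised constructs.

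Nothing here bears on Aim 1. A reader might extend the doubt to whether the intervention raises vaccination, but those comparisons are between randomised arms and do not use the constructs. The point should be settled before the Aim 2 analysis is run.

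**What to change.** In Section 2.m., Aim 2, state that:

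1. The mediator is the post-exposure construct at a named time point that precedes the vaccination being explained, for example T2.
2. Each mediator equation and the outcome equation include the T1 values of the constructs and a prespecified set of screener/T1 covariates, for example routine check-up, disclosure to a provider, relationship status, urban residence and age. These terms are not subject to pruning.
3. Bare change scores are not used.
4. A sensitivity analysis shows how strong an unmeasured construct–outcome confounder would have to be to remove each indirect effect, and the key-drivers conclusion is worded as conditional on no such confounding.

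The pointer to Section 2.n. should be replaced by a list of the constructs.

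Cost: SAP wording and a larger model, with no new data. The interval for the construct-to-vaccination path widens by about 1/√(1−r²), which is 1.15 at r = 0.5 and 1.40 at r = 0.7 for one mediator. A T2 mediator also cannot carry any effect of the reminders, which begin one month after randomisation (Sections 2.f. and 2.g.). If that effect is of interest, a later mediator needs its own statement of how doses received before its measurement are treated.

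### Aim 3 judges moderation only by an odds-ratio interaction; if control uptake differs by moderator level, that alone cannot show where more men gain

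*Combined protocol and SAP*

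**What the plan says.** Section 2.m, Aim 3 (Moderation), states the hypothesis as: "We hypothesize intervention effects will be stronger (i.e., moderation) among YSMM who are not married or in a relationship". The other three favoured groups are urban residents, men with a recent check-up, and men who have disclosed their orientation to a provider. The paragraph does not say on what scale an effect counts as stronger.

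The analysis is: "We will use logistic regression models that include an interaction term between each potential moderator and study arm". Its output is given as "Logistic regression models will produce ORs and 95% CIs". An interaction is declared when the term has p below 0.05; sidedness is not stated, and I take it as two-sided. The power statement is on the same scale: "Given our analytic sample size, we will have 80% power to detect interaction terms with ORs>2.30".

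Two of the stated reasons are that some men "live in urban areas (due to greater access to care, including LGBT-friendly providers" and that others "report having a routine medical check-up in the last year (due to higher utilization of healthcare and self-efficacy to get HPV vaccine". For disclosure the reason is greater confidence in talking with a provider about the vaccine. For relationship status it is perceived vulnerability.

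The descriptive proportions with 95% CIs in Section 2.m belong to Aim 1 and are not planned by moderator level. Aim 1 projects control, Out-U and Out-I rates of 20%, 35% and 45% for initiation, and 10%, 22% and 35% for completion. No rate is given by moderator level.

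**The concern.** The logistic product term estimates a ratio of odds ratios. At rates between 10% and 45%, the same gain in percentage points gives a smaller odds ratio when it starts from a higher control rate. Access to care, healthcare use and ease with providers could each help a man get vaccinated without the intervention. If so, the favoured group starts higher and the odds-ratio scale works against Hypothesis 3. Its men could gain as many points as the others, or more, while the interaction falls at or below 1.

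Aim 3 is meant to establish whether efficacy differs by participant characteristics. Someone deciding where to offer the programme would want to know how many more men are vaccinated in each group. An odds-ratio interaction alone could point away from that answer.

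**Working it through.** **Inputs.** From Section 2.m: 700 per arm and 70% retention, so 700 x 0.70 = 490 analysed per arm; the projected rates above; p below 0.05. Assumed, because the documents do not give them: a binary moderator split 50/50 (245 men per arm-by-moderator cell), and control rates by moderator level centred on the projected control rate.

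**Formulas.** Log interaction OR = ln(OR favoured / OR other). SE = sqrt of the sum over four cells of 1/(n p (1-p)). Chance of a significant reversal = P(Z < -1.96 - lnIOR/SE), where IOR is the interaction OR.

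**The plan's own figure first.** Initiation, control vs Out-U, marginal rates in both levels: SE = sqrt(2 x [1/(245 x 0.20 x 0.80) + 1/(245 x 0.35 x 0.65)]) = sqrt(2 x [0.0255 + 0.0179]) = 0.295. Detectable OR = exp((1.96 + 0.84) x 0.295) = 2.28. The stated 2.30 is reproduced for initiation, so the set-up is close to the plan's own.

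**One case in full.** Completion, Out-I, control 13% (favoured) vs 7% (other), +25 points in both:
- OR favoured = (0.38/0.62)/(0.13/0.87) = 4.10; OR other = (0.32/0.68)/(0.07/0.93) = 6.25; IOR = 0.66, ln = -0.42.
- SE = sqrt(0.0361 + 0.0173 + 0.0627 + 0.0188) = 0.367.
- P(Z < -1.96 + 1.15) = 0.21. Binomial simulation gives 19.5%. A significant favourable result occurs in about 0.1%.

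**Equal absolute gains, other cases** (analytic values and simulations agree within about 2 points):

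| Outcome, contrast with control | Control, favoured vs other | Gain in both | IOR | Significant reversal |
|---|---|---|---|---|
| Initiation, Out-U | 23% vs 17% | 15 | 0.89 | about 6% |
| Initiation, Out-U | 25% vs 15% | 15 | 0.82 | about 9% |
| Initiation, Out-I | 25% vs 15% | 25 | 0.79 | about 12% |
| Completion, Out-U | 12% vs 8% | 12 | 0.81 | about 8% |
| Completion, Out-U | 13% vs 7% | 12 | 0.72 | about 14% |
| Completion, Out-I | 12% vs 8% | 25 | 0.76 | about 12% |
| Completion, Out-I | 13% vs 7% | 25 | 0.66 | 19-21% |
| Completion, Out-I | 14% vs 6% | 25 | 0.56 | 32-34% |
| Any | equal | equal | 1.00 | 2.5% (nominal) |

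**Larger gain in the favoured group.** Completion, Out-I, 13% to 42% (+29) vs 7% to 28% (+21): IOR = 0.94, and the test finds favourable moderation in 1.7% of trials. Conversely, a common OR of 4.85 on controls of 13% and 7% gives 42.0% and 26.7%, gains of 29.0 and 19.7 points that would read as no moderation.

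**The additive contrast in the same cases.** SE of the difference in risk differences = sqrt of the sum of p(1-p)/n. For +29 vs +21: sqrt((0.1131 + 0.2436 + 0.0651 + 0.2016)/245) = 0.050, so 0.08/0.050 is about 1.59 and power is about 36%. For 29.0 vs 19.7 points it is about 46%. Under equal gains it errs at about 2.5% per side.

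**The case against.** The strongest reply is that the plan does name a scale. Aim 3 specifies logistic interaction terms, odds ratios with CIs, a significance threshold and a detectable interaction OR, and Aim 1 also reports efficacy as odds ratios. Effect modification depends on scale whichever scale is chosen. This stands: the planned test is legitimate and need not be replaced.

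A reader might infer that the plan's rationales imply unequal control rates. They do not. They explain why the intervention should work better in certain men and say nothing about uptake without it. Eligibility (Section 2.a) excludes anyone with a prior dose, so men with recent check-ups who remain unvaccinated are a selected group whose control uptake could differ either way. The inference does not reach relationship status at all. This also stands, and is why the point is conditional.

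A reader might also infer that Aim 3 will usually report the opposite of the truth. The figures do not support that. Mild cases give 6-9% reversal, and even at 13% vs 7% for completion with Out-I about 80% of trials declare no interaction, which is the right answer on the additive scale when gains are equal.

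What survives is narrower. Nothing planned for Aim 3 would show a reader that a null or reversed odds-ratio interaction sits beside equal or larger absolute gains.

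**Conclusion.** The point holds as a gap in defining and interpreting *stronger*, not as an error in the test or its power figure. It is conditional on control rates differing by moderator level, which the documents neither state nor exclude, and the sizes rest on 490 per arm and a 50/50 split. Under those assumptions and equal gains, significant reversal is uncommon for initiation (about 6-12% at gaps of 6-10 points) and for completion with Out-U at 12% vs 8% (about 8%). It is material for completion with Out-I (about 19-34% at gaps of 6-8 points). Missed moderation is the other cost: 1.7% detection when the true gains are 29 vs 21 points. The Aim 1 efficacy comparisons are unaffected. This is a cheap improvement worth making.

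**What to change.** In Section 2.m, Aim 3:

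- Keep the logistic interaction test and state that it tests moderation on the odds-ratio scale.
- From the same fitted models, report for each moderator level the standardised vaccination probability by arm, the risk difference for each arm contrast, and the difference between risk differences with a 95% CI (delta method or bootstrap).
- Base any statement about where more men are vaccinated on that CI. Describe results that differ between scales as scale-dependent.

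A tempting shortcut is to accept an odds-ratio interaction whenever the estimated difference in risk differences has the same sign. It should not be used. In simulation it cuts reversals only from 19.5% to 19.1% (completion, 13% vs 7%), from 32.3% to 30.3% (14% vs 6%), and not at all from 11.6% (initiation, 25% vs 15%). Detection in the 29-vs-21-point case stays at 1.7%.

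The cost is a few sentences and a post-estimation step, with no new data. It adds one interval per moderator and contrast for each outcome: for the four named moderators, 4 x 3 contrasts x 2 outcomes = 24. Precision is limited, with about 36-46% power for a difference of 8-9 points on completion, so many of these intervals will be inconclusive and should be reported as such.
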